6.7 OTHER MEDICATIONS

6.7.1 Permitted Medications

Other medications, apart from those listed in 6.7.2, will be allowed. All concurrent medication(s) will be recorded.

6.7.2 Prohibited Medications

Repaglinide, and other anti-diabetic drugs in this class are contra-indicated due to the increased risk of hypoglycaemia. Thiazide diuretics due to increased risk of hyper diuresis. These medications are prohibited in this trial. The GP information letter and PIS will contain information on all the above points.

6.7.3 Concomitant Medications

Details of all concomitant medications will be discussed and recorded in the CRF at all study visits, including telephone visits.

6.8 DISCONTINUATION

The trial medication will be discontinued due to safety and/or tolerability in the following circumstances:

- Participant becomes pregnant
- LFTs rise to greater than twice the normal range
- Participant develops symptoms of NYHA class IV heart failure
- Participant has vomiting and diarrhoea for 48 hours and volume depletion is suspected
- Participant develops symptomatic postural hypotension
- Participant develops signs of vulvovaginitis, balanitis and related genital infections or urinary tract infections which do not respond to treatment.
- Participant has suspected or diagnosed Diabetic Ketoacidosis
- Participant develops a sustained eGFR < 45 mls/min despite alteration of dose of furosemide or alternative loop diuretic

7 TRIAL ASSESSMENTS

7.1 TRIAL ASSESSMENTS

As outlined in section 5.2, participants will be provided with a full PIS and are given at least 24 hours to consider their response before a screening visit will be arranged for consent to be taken and to check their eligibility by all the criteria. On discussion with the participant, if they are willing to wait for the results of their safety blood tests, visit 1 (screening) and visit 2 (baseline/randomisation) will be offered to be combined.

For details of assessments carried out at each visit see Appendix 1

8 DATA COLLECTION& MANAGEMENT

8.1 DATA COLLECTION

The data will be collected by the PI or delegate on a paper case report form (CRF) with subsequent transcription to an electronic CRF. Electronic storage will be in an encrypted form on a password protected device.

The medical notes will act as source data for past medical history and blood results. Any data relating to general medical history will be documented in the notes.

8.2 DATA MANAGEMENT SYSTEM

Excel will be used as the data management system (DMS) with adherence to TASC SOP 48 Data Management in CTIMPs using Excel, by the trial team doing the data entry and analysis.

The DMS will be based on the protocol and CRF for the trial and individual requirements of the investigators. Development and validation of the trial database and QC will be done according to TASC SOP 48.

9 STATISTICS AND DATA ANALYSIS

9.1 SAMPLE SIZE CALCULATION

9.1.1 POWER CALCULATIONS

Power calculations are based on our previous data in participants with CHF³⁶⁻⁴⁰ as well as more contemporary data.41 The sample size is based on the mean furosemideinduced urinary volume (SD=250). A 20% increase is expected in this parameter following SGLT2 inhibition. This increase in urinary volume is based on published percentage increases in urinary volume in T2D patients that range from 11%-33% depending on the dose of the SGLT2 inhibitor as shown by List and colleagues⁴² in the available data with dapagliflozin (dapagliflozin 2.5 mg: 11% increase in 24-hr urine volume; dapagliflozin 5 mg: 22% 11% increase in 24-hr urine volume; dapagliflozin 10 mg: 24% 11% increase in 24-hr urine volume; dapaqliflozin 20 mg: 27% 11% increase in 24-hr urine volume and dapagliflozin 50 mg: 33% 11% increase in 24-hr urine volume). There is no data of SGLT inhibition together with loop diuretics apart from the previously discussed case report of a diuretic resistant HF patient in whom the fluid overload was successfully treated with the SGLT2 inhibitor, ipragliflozin. The authors reported a striking 50% increase in urinary volume (following treatment with 50 mg daily of oral ipragliflozin for 5 days).34 Based on the above, it was determined that a 20% increase in furosemide induced increase in urinary volume will be reasonable.

With an alpha 0.05 and power of 90%, 22 participants per arm are required, assuming 35% drop out. Since this trial is using an AB/BA crossover design, a total of 34 participants will be required, as each participant will be exposed to both arms of the

trial. The rationale for the high dropout rate, is due to the high intensity renal physiological tests that will occur on 4 occasions for the participants, from 0730 to 1230 we feel that anything less than a 35% drop out rate would be conservative.

9.2 PROPOSED ANALYSES

9.2.1 STATISTICAL ANALYSIS

Participants will be allocated to treatment groups at random. Descriptive statistics will be calculated for all data and reported as mean (SD) for continuous data and N (%) for categorical data. For statistical evaluation of repeated measurements, analysis of variance will be used. P<0.05 will be taken as the level of statistical significance.

A detailed statistical analysis plan will be prepared during the trial by the trial statistician.

9.3 MISSING DATA

The primary analysis will be based on the intention-to-treat principle. The extent of missing data will be examined and the reason for the dropout ascertained. Multiple imputation may be used to impute missing values if necessary and where assumptions for missing at random (MAR) data are met. Complete case analysis where missing participants are excluded will be carried out as a secondary analysis. Pre-specified sub-group analyses will be completed by fitting the appropriate interaction term in the regression model and- if significant outcomes will be presented separately by level of sub-group.

With regards to participant medication, this will be recorded at baseline and at each trial visit with a secondary analysis adjusting for changes in trial medications planned.

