## **7.3 Covariates and Subgroups**

Covariates that may have an influence on the end points listed include gender, BMI, age and treatment order received i.e. placebo/empagliflozin versus empagliflozin/placebo. As the study is a crossover in design, the treatment order was included in the initial analysis as a covariate to ascertain if the intervention being investigated has a sustained effect on the primary outcome despite the 2 week washout period. These demographic subgroups were analysed for different treatments effects (for example comparison of effects by age, gender, BMI and treatment order). Where possible forest plot figures were used to communicate the relevant information about possible subgroup effects and interactions.

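### Subgroup results are shown by level only if the interaction is significant, so with 22 to 34 participants whatever passes is exaggerated; report every interaction estimate and label the analyses exploratory

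*Protocol*

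**What the plan says.** The subgroup rule sits in Protocol 9.3, under the missing-data heading: "Pre-specified sub-group analyses will be completed by fitting the appropriate interaction term in the regression model", and then "if significant outcomes will be presented separately by level of sub-group". That section names no factors and no threshold. The only significance level is the general one in Protocol 9.2.1: "P<0.05 will be taken as the level of statistical significance".

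The factors appear in SAP 7.3, which describes a "for example comparison of effects by age, gender, BMI and treatment order". On display the same section says: "Where possible forest plot figures were used to communicate the relevant information about possible subgroup effects and interactions". It does not repeat the protocol's condition on significance, and does not cancel it.

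Neither document labels these analyses exploratory, adjusts for the number of tests, gives cut-points for age or BMI, or states which endpoints the subgroup analyses cover.

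**The concern.** Testing the interaction before looking within subgroups is good practice. The difficulty is making display depend on the result. With few participants, an interaction estimate can reach P<0.05 only by being very large, so the level-specific effects that get shown are those that chance has pushed furthest apart. A reader would see one group with a strong diuretic response and another with little, and no sign that the display was selected.

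Protocol 1.2 says the trial is meant to supply data for the design of later studies. A selected and exaggerated contrast by age, gender or BMI is the sort of result that could wrongly shape their eligibility or stratification.

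The two documents also leave two readings open, showing all subgroups (the forest plots) or showing only the significant ones (the protocol rule), and nothing prevents the choice being made after the results are known.

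**Working it through.** **Number analysed.** Protocol 9.1.1: "With an alpha 0.05 and power of 90%, 22 participants per arm are required, assuming 35% drop out", with 34 recruited. Check: 22/(1 − 0.35) = 33.8, rounded up to 34; in reverse, 34 × 0.65 = 22.1. So 22 is the planned number of completers and 34 is taken as the upper limit. The 22 itself cannot be rebuilt, because the mean to which the 20% increase applies is not given.

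**Scale.** Work with within-participant differences (empagliflozin minus placebo) in units of their SD. A paired t-test with 22 participants, two-sided 0.05 (sidedness assumed) and 90% power needs a mean difference of 0.725 SD. This is taken as the true effect, equal in everyone.

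**Size of interaction needed to pass the gate.** Two levels of sizes a and b are compared by a t-test. At an average SD the difference must exceed t × √(1/a + 1/b).
- 11/11 (20 df): 2.086 × √(2/11) = 2.086 × 0.426 = 0.889 SD; 0.889/0.725 = 1.23 times the whole planned treatment effect.
- 17/17 (32 df): 2.037 × √(2/17) = 2.037 × 0.343 = 0.699 SD; 0.699/0.725 = 0.96 times.

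**What is shown once the gate is passed.** These are simulated means of the lower and higher level as a share of the true effect, given a significant interaction and no true interaction. Repeat runs agree to within about one percentage point.

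| Split | Lower level | Higher level |
|---|---|---|
| 11/11 | 35% | 166% |
| 17/17 | 46% | 154% |

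Part of any gap comes simply from calling one level lower and the other higher. Without a gate at 11/11, the expected absolute difference is 0.426 × √(2/π) = 0.340 SD. Half of that is 0.170, and 0.170/0.725 = 0.23, so the levels average about 77% and 123%. The gate moves them from there to 35% and 166%.

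In about 88% of the gated 11/11 cases the lower level is itself non-significant (73% at 17/17). A level of 11 chosen in advance would be non-significant about 42% of the time.

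**When a modest interaction is real.** With true effects of 1.25 and 0.75 times the mean at 11/11, power is about 13%, and the significant interaction estimates average about 2.8 times the truth.

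**Chance of at least one false interaction.**
- Primary endpoint; age, gender and BMI: 1 − 0.95³ = 14.3% if independent; by simulation 12.5% at correlation 0.5 and 9.8% at 0.8 (correlations assumed).
- Counting treatment order as a fourth factor: 1 − 0.95⁴ = 18.5%.
- Three factors by seven endpoints (one primary, six secondary; Protocol 2.2, SAP 4.2), 21 tests: 1 − 0.95²¹ = 66% if independent, 43% at correlation 0.5, 23% at 0.8.

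**The case against.** The strongest reply is that the SAP is the more detailed document and plans forest plots, which normally show every level whatever its P value. That would reduce selective display. But the plots are promised only where feasible and the protocol rule is not withdrawn, so the reply narrows the point without removing it.

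Four stronger inferences are tempting, and the documents do not support them.
- **That false subgroup findings would be frequent.** On the primary endpoint over three factors the chance is about 10% to 14%.
- **That the SAP orders 21 tests.** The plural wording belongs to a different sentence, on adjustment: "Covariates that may have an influence on the end points listed include gender, BMI, age and treatment order received". The subgroup sentence names no endpoint, and the only outcome named in SAP 7.3 is the primary. Testing all seven is permitted, not stated.
- **That a subgroup claim is planned.** Presenting results by level is not a claim. Protocol 3.2.3 calls the trial proof of concept, and Protocol 14.5 says confirmatory studies are needed.
- **That small numbers raise the false-positive rate.** Each test keeps its 5% level. Small numbers lower power and enlarge the estimates that pass.

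It is also fair to say that 22 is the low end: Protocol 5.5.4 replaces withdrawals where possible and Protocol 9.3 allows imputation. At 34 the distortion is smaller but still substantial.

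**Conclusion.** The point holds as a reporting weakness. The protocol's gate is still in force, carries no exploratory label, and selects exaggerated estimates: about 35% and 166% of a uniform true effect at 11/11, and 46% and 154% at 17/17.

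These figures assume two-sided 0.05 applied to interactions (inferred from the general rule), an effect of 0.725 SD of the within-participant difference, even splits and normal data. The bias under selection does not depend on how many endpoints are tested; the chance of a false interaction does.

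The primary treatment comparison and the sample size are untouched, so this is an inexpensive improvement and not a flaw in the main result.

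**What to change.** Replace the conditional sentence in Protocol 9.3 and align SAP 7.3 to say:
- Subgroup analyses are exploratory and confined to the primary endpoint.
- The treatment-by-factor interaction estimate with its 95% CI is reported for gender, age and BMI whatever the P value.
- For gender, the treatment effect is shown at each level. Age and BMI enter as continuous terms, with the predicted effect shown at values fixed in advance, such as the quartiles, so no cut-points are needed.
- Treatment order is a design term in the crossover model and not a subgroup. In a two-period crossover, a difference in treatment effect between the two orders reflects period and carryover effects, not a type of patient.
- No subgroup-specific conclusion is drawn.

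The cost is a wording amendment to the protocol and the SAP; forest plots are already planned. No extra participants, data or change of alpha are needed. The price is that no subgroup effect can be claimed as established, which these numbers would not support anyway.

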10 ADVERSE EVENTS

Adverse event reporting will be carried out in accordance with TASC SOP 11: Identifying, Recording and Reporting Adverse Events for Clinical Trials of Investigational Medicinal Products. The CI (or delegate) is responsible for detection and documentation (and reporting, where required) of adverse events.

10.1 DEFINITIONS

An **adverse event** (AE) is any untoward medical event affecting a clinical trial participant. Each initial AE will be considered for severity, causality or expectedness

and may be reclassified as a serious event or reaction based on prevailing circumstances.

An **adverse reaction** (AR) is where it is suspected that an AE has been caused by a reaction to a trial drug.

A serious adverse event (SAE), serious adverse reaction (SAR) or suspected unexpected serious adverse reaction (SUSAR) is any AE, AR or UAR that at any dose:

- results in death
- is life threatening
- requires hospitalisation or prolongation of existing hospitalisation
- results in persistent or significant disability or incapacity
- is a congenital anomaly or birth defect
- Or is otherwise considered serious

Note: Hospitalisations for treatment planned prior to randomisation and hospitalisation for elective treatment of a pre-existing condition will not be considered as an SAE. However, any adverse events occurring during such hospitalisation will be recorded.

10.2 DETECTING AES AND SAES

The CI is responsible for the detection and documentation of events meeting the criteria and definitions below.

Full details of contraindications and side effects that have been reported following administration of the trial drug can be found in the SmPC. Adverse reactions in association with empagliflozin are rare in the overall treated population and mostly of a minor nature. The incidence may be higher in the presence of renal and/or hepatic disorder.

Common non-serious side effects are: Runny or stuffy nose; sore throat.

Severe side effects that may occur and which immediate attention should be sought are: Severe allergic reactions (rash; hives; itching; difficulty breathing or swallowing; tightness in the chest; swelling of the mouth, face, lips, throat, or tongue; unusual hoarseness); fainting; fast or irregular heartbeat; increased urination; muscle weakness; penis discharge, redness, rash, itching, pain, or swelling; severe or

persistent headache, dizziness, or light-headedness; sluggishness; symptoms of low blood sugar (e.g. confusion, increased sweating, weakness, tremors, dizziness, fainting, drowsiness, headache, irritability, chills, fast heartbeat, vision changes, increased hunger); symptoms of kidney problems or urinary tract infection (e.g. blood in the urine, change in the amount of urine produced, difficult or painful urination, unusual or persistent pain in the mid to lower back, unexplained swelling); unusual tiredness or weakness; vaginal discharge, itching, or odour, very dry mouth or eyes.

Participants should be instructed to contact a member of the trial team at any time after consenting to join the trial if any of the above symptoms develop. All reported adverse events (AEs) that occur after joining the trial will be recorded in detail in the CRF AE log. In the case of an AE, the Investigator should initiate the appropriate treatment according to their medical judgement. Participants with AEs present at the last visit must be followed up until resolution of the event.

10.3 RECORDING AND REPORTING AES AND SAES

All AEs and SAEs will be recorded from the time a participant consents to join the trial until the last trial visit. Participants with unresolved AEs at their last trial visit will be followed up until resolution or 30 days after their last visit, whichever is sooner. SAEs and SUSARS will be followed until resolution.

The CI or delegate will ask about the occurrence of AEs and hospitalisations at every visit during the trial. AEs will be recorded on the AE Log in the CRF. SAEs will be submitted on an SAE form to the TASC Pharmacovigilance Section ([contact]) within 24 hours of becoming aware of the SAE. SAEs will be initially assessed for causality and expectedness by the Investigator. The Sponsor will make the definitive assessment on expectedness. The evaluation of expectedness will be made based on the knowledge of the reaction and the relevant product information (SmPC). Refer to TASC SOP 11 "Identifying, Recording and Reporting Adverse Events for CTIMPs".

10.4 EVALUATION OF AES AND SAES.

Seriousness, causality, severity and expectedness will be evaluated as though the participant is taking an active drug.

10.4.1 Assessment of Seriousness

The CI or delegate will make an assessment of seriousness as defined in section 10.1.

10.4.2 Assessment of Causality

The CI or delegate will make an assessment of whether the AE is likely to be related to treatment according to the following definitions.

Unrelated: where the AE is not considered to be related to the trial drug.

Possibly: although a relationship to the trial drug cannot be completely ruled out, the nature of the event, underlying disease, concomitant medication or temporal relationship make other explanations more likely.

Probably: the temporal relationship and absence of a more likely explanation suggest the event could be related to the trial drug.

Definitely: the known effects of the trial drug or its therapeutic class, or based on challenge testing, suggest that the trial drug is the most likely cause.

All AEs/SAEs judged as having a reasonable suspected causal relationship (e.g. possibly, probably, definitely) to the trial drug will be considered as ARs/SARs. All AEs/SAEs judged as being related (e.g. possibly, probably, definitely) to an interaction between the trial drug and another drug will also be considered to be ARs/SARs.

Alternative causes such as natural history of underlying disease, concomitant therapy, other risk factors and the temporal relationship of the event to the treatment will be considered. The blind will not be broken for the purpose of making this assessment.

10.4.3 Assessment of Severity

The CI or delegate will make an assessment of severity for each AE according to one of the following categories:

Mild: an event that is easily tolerated by the participant, causing minimal discomfort and not interfering with every day activities.

Moderate: an event that is sufficiently discomforting to interfere with normal everyday activities.

Severe: an event that prevents normal everyday activities.

Note: the term 'severe', used to describe the intensity, should not be confused with 'serious' which is a regulatory definition based on participant/event outcome or action criteria. For example, a headache may be severe by not serious, while a minor stroke is serious but may not be severe.

10.4.4 Assessment of Expectedness

If an event is judged to be an AR/SAR, the evaluation of expectedness will be made based on knowledge of the reaction and the relevant product information documented in the SmPC Section 4.8.

ARs/SARs may be classed as either:

Expected: The AR is consistent with the toxicity of the trial drug listed in the SmPC.

Unexpected: The AR is not consistent with the toxicity in the SmPC.

10.5 REPORTING OF SAES/SURS/SUSARS

SAEs must be reported to the TASC Pharmacovigilance Section [contact] within 24 hours of the CI or delegate becoming aware of the event. The TASC SAE form must be completed as thoroughly as possible with all available details of the event and signed by the Investigator. If any of the information is not available at the time of reporting, the Investigator will ensure that any missing information is provided on a follow-up SAE form as soon as this becomes available. It will be indicated on the form that this information is follow-up information of a previously reported event.

All SAEs must be followed up to resolution and any additional information reported to the TASC Pharmacovigilance Section [contact] using the TASC SAE form.

10.6 REGULATORY REPORTING REQUIREMENTS

The Sponsor is responsible for reporting SUSARs to the competent authority, the MHRA, the Research Ethics Committee (REC) and any other competent authorities. Fatal or life threatening SUSARs will be reported within 7 days and non-fatal and non-life threatening SUSARs within 15 days.

10.7 ANNUAL REPORTING REQUIREMENTS

The following reports will be submitted each year as a condition of the authorisation to undertake a clinical trial or as a condition of a favourable opinion from REC.

The Development Safety Update Report (DSUR) will be prepared by the Sponsor - TASC Pharmacovigilance Section - and CI and submitted to the MHRA on the anniversary date of Clinical Trial Authorisation (CTA).

An NRES CTIMP Safety Report Form will be sent to REC along with the DSUR. Reports of SUSARs in the UK, urgent safety measures and any other safety reports submitted, for example reports of a data monitoring committee, will also be accompanied by a Safety Report Form.

A NRES Annual Progress Report for CTIMPs will be prepared and submitted by the CI to REC and copied to sponsor on the anniversary date of the REC favourable opinion.

